1.3.1 Risk-Benefit Balance

The risks associated with participating in this controlled feeding experiment are low. The diets will be constructed to meet all nutritional requirements. The CMC will be purchased from Modernist Pantry and is the same as that which is sold to small bakeries throughout the United States. Thus, consumption of the study diet entails no greater risk than consumption of a typical American diet outside of the study procedures.

Participants will undergo phlebotomy and sigmoidoscopy with biopsy. There is a small potential risk for complications of sigmoidoscopy, including bleeding and perforation. The risks of these complications are estimated to be less than 1% for bleeding and less than 0.1% for perforation. Patients with contraindications to biopsy will be excluded. The risks of phlebotomy include bleeding, infection, phlebitis, and fainting. As with all research, there is a small risk of loss of confidentiality. Participants may also experience some discomfort associated with eating a limited diet for 14 days. Participants may also feel tired and/or discomfort from staying in the hospital for the 11 day inpatient stay.

In summary, the risk of serious or severe adverse events is likely extremely low. While there is no direct benefit expected for the participants, the balance of the participants' risk vs. the knowledge to be gained is believed to be favorable.

2 Study Objectives

The specific aims for our proposal are:

1. Establish a tractable and physiologic means of administering and measuring CMC consumption and its metabolic impact in healthy volunteers.
2. Examine extent to which CMC consumption impacts human gut microbiota composition, gene expression, and/or localization.
3. Explore effects of CMC consumption on a range of inflammatory and metabolic parameters that characterize metabolic syndrome.

3 Study Design

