4.4 Early Withdrawal of Participants

4.4.1 When and How to Withdraw Participants

Participants may be withdrawn from the study at any time if the investigator or the participant believes that the participant's safety will be jeopardized by continued participation, or if the participant does not follow study procedures. Likewise, participants will be withdrawn from the study if they withdraw consent.

5 Study Intervention

All foods will be prepared within the CHPS's metabolic kitchen without emulsifiers (unless specifically added). All participants will follow the same Western style diet (i.e. the only difference being portion size). The macronutrient percentages of calories for the study diet will be 55% carbohydrate, 30% fat, and 15% protein. The diet will be composed of two menus that will be consumed on alternating days. Water, coffee and tea will be provided as desired. Participants will have access to additional food outside of the meals provided, however, the entire serving of the previous meal must have been consumed. The additional food provided outside of the scheduled meals will consist of the food from the same Western style diet provided for each meal.

For the three days prior to admission, participants will be eating an emulsifier free diet at home. Food will be provided by the CHPS metabolic kitchen. After admission to CHPS, no emulsifiers will be consumed prior to dinner on Day 1. Thus, accounting for the 8 hours of nil per os status prior to admission, all participants will have approximately 80 hours of emulsifier free washout time prior to administration of the food containing CMC.

Participants will be randomly assigned to receive 0 or 15 gm per day of CMC (8 participants in each arm of the study). Beginning with the dinner meal on Day 1, all participants will consume one serving of brownie or sorbet (15 gm) per day that contain 0 or 2.5 gm CMC per serving. The brownie and sorbet servings will be provided at all three scheduled meals and scheduled snacks. Prior to eating any other food on the study menu, participants must consume the brownie and sorbet servings.

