6.1.3 Stool sample collection

Stool will be collected from the inpatient participants daily. Only the first sample of each day will be aliquoted and frozen. Subsequent samples (if available) will be weighed and the weight will be recorded. Each stool specimen that is collected will be processed in the same manner. The participant will be provided with a collection device to be placed in the commode that allows for separation of urine and feces, and keeps the feces separated from the toilet water. After they have finished voiding their first stool of the day, the specimen will be immediately processed according to the following protocol by the CHPS nurses. Using vials with small spoons attached to the lid, a small amount of stool will be scooped on to the spoon from the surface of the stool sample and leveled off with a tongue depressor. The weight of the sample will be recorded. A minimum of seven samples will be obtained from one stool collection. All samples will be labeled with the subject ID #, and the date of collection from the volunteer. The core sample will be labeled the same way. The aliquoted samples and the core sample will be immediately frozen at minus 80°C. The nurses will rate the sample based on the Bristol Stool Chart. Residual stool samples will be stored into up to five 15ml coring vials. Subsequent stools will be weighed in the collection device, rated on the Bristol Stool Chart, and then discarded.

In order to have a baseline stool sample prior to study diet, participants will be required to collect a stool sample prior to the post-screening visit. Participants will also collect a stool sample on the day prior to admission to CHPS. Study staff will provide the participant with collection materials and instructions for collecting the stool at home and bringing it in to study staff. Immediately after voiding the sample, the participant will put a small amount of stool into a spoon-top vial containing ethanol. They will label this vial and the collection device containing the remainder of the stool sample with the date of collection, and will rate the stool on the Bristol Stool Chart. They will then arrange a drop-off time with the study coordinator within 48 hours of sample collection. The study coordinator will bring this stool sample to the study lab on the 9th floor Biomedical Research Building (BRB). Lab personnel will aliquot the stool sample into a minimum of 7 spoon-top vials.

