7.2.1 Determining the effect of CMC on fecal and mucosal microbiome composition

We will first compare the bacteria taxa in each fecal stool communities sampled at baseline, after the 3 day emulsifier free period and during the intervention period (total of 96 stool samples and 16 biopsy samples per treatment arm – 8 participants on each diet) to determine within-diet and between-diet variation prior to the administration of antibiotics. The analyses will be conducted separately for microbiomes in fecal samples and also in colonic mucosa samples. We will employ both of our methods (PCoA and proportion of the community represented by different taxa) to summarize the data at each time point. Besides comparing the microbiome among the treatment groups at day 11, we will also perform repeated measurement analysis of variance (RM-ANOVA) to study the time effects on microbiome and potential time and diet interaction effects for our data on fecal samples. The outcomes of such RM-ANOVA are the significant principal components summarizing the bacterial taxa.

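### Section 7.2.1 names no baseline-adjusted estimate of the CMC effect on fecal composition; one pre-specified on-CMC versus pre-CMC contrast should be added beside the RM-ANOVA

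*Combined protocol and SAP*

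**What the plan says.** Objective 2 (Section 2) is to "Examine extent to which CMC consumption impacts human gut microbiota composition, gene expression, and/or localization". Section 7.2.1 describes stools "sampled at baseline, after the 3 day emulsifier free period and during the intervention period", with a "total of 96 stool samples and 16 biopsy samples per treatment arm". It then names two between-arm analyses of fecal composition:

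- a comparison at one time point ("Besides comparing the microbiome among the treatment groups at day 11"), with no adjustment for earlier stools mentioned;
- an RM-ANOVA on principal components, "to study the time effects on microbiome and potential time and diet interaction effects for our data on fecal samples".

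The opening sentence of 7.2.1 also speaks of comparing taxa across the three phases, but attaches no test to this. The section gives no time coding, degrees of freedom, contrast, covariance structure or sphericity correction.

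**The concern.** Objective 2 asks about extent, so it needs a direction and a size: how much more does composition move from before CMC to on CMC in the CMC arm than in the control arm? That is a question with one degree of freedom. An omnibus time-by-diet test asks instead whether the arm difference takes any pattern over all occasions. A significant result gives no direction or size, and an irregular day-to-day pattern can produce one. The Day 11 comparison does give a direction, but it uses one stool per person and none of the pre-CMC stools. With 8 participants per arm, a lasting shift could be missed by both tests although the stools already collected would show it.

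**Working it through.** **Inputs from the documents.** There are "8 participants in each arm of the study" (Section 5). 96 / 8 = 12 stools per participant, which matches one at Visit 2 plus daily inpatient stools on Days 1-11 (Section 6.1.3: "Stool will be collected from the inpatient participants daily"). Section 5 states that "no emulsifiers will be consumed prior to dinner on Day 1", so 2 occasions precede CMC (Visit 2, Day 1) and 10 follow it (Days 2-11).

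**Assumptions, not in the documents.** Two-sided alpha of 0.05; effect size, time course and within-person correlation for this outcome.

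**The plan's own figures.** Section 7.1 states no power for fecal composition. A two-sample t-test on 14 df at 0.05 reproduces its other figures: 1.51 SD gives 80.2% (stated 80%); the paired 1.15 SD gives 79.6% (stated 80%); Aim 2 gives 89.7% and 79.3% (stated 90% and 80%). The assumed alpha therefore fits.

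**Immediate, sustained step, equal within-person correlations.** Let δ be the shift and σ the within-person SD. Both longitudinal tests have the same noncentrality:

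λ = (n/2) × (2 × 10 / 12) × (δ/σ)² = 4 × 1.667 × (δ/σ)² = 6.67 (δ/σ)²

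- Contrast (mean of 10 on-CMC stools minus mean of 2 pre-CMC stools): F(1, 14), since 16 − 2 = 14. Power of 80% needs λ = 9.08, so δ/σ = √(9.08 / 6.67) = 1.17.
- Interaction: (2 − 1)(12 − 1) = 11 and (16 − 2)(12 − 1) = 154 df. F(11, 154) at λ = 9.08 has 44.6% power.
- Day 11 alone: the standardised difference is 1.17 × √(1 − ρ), where ρ is the between-person share of variance. Power is 44%, 34% and 22% at ρ = 0.3, 0.5 and 0.7. Allowing serial correlation raises the top of the range to about 46%.

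The ratio of interaction to contrast power changes with the effect size:

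| Contrast power | Interaction power | Ratio |
|---|---|---|
| 50% | 21% | 0.43 |
| 70% | 35% | 0.50 |
| 80% | 45% | 0.56 |
| 90% | 59% | 0.66 |
| 95% | 71% | 0.75 |

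The occasion count matters little: with 11 or 13 occasions the interaction has 46% or 43% when the contrast has 80%.

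**Sphericity correction, same step, by simulation.** The effect is set so that the contrast keeps about 80%:

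| Lag-1 residual correlation | 0 | 0.3 | 0.5 | 0.7 |
|---|---|---|---|---|
| Greenhouse-Geisser | 28% | 33% | 40% | 48% |
| Huynh-Feldt | 44% | 49% | 53% | 57% |

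Uncorrected, the interaction reaches 49% to 61% at correlations of 0.3 to 0.6, but its type I error rises to as much as 0.06 to 0.08.

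**Other time courses, same peak effect.** The middle column assumes sphericity and no correction, except that the two onset rows also cover serial correlation:

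| Time course | Interaction, uncorrected | Interaction, corrected | Contrast |
|---|---|---|---|
| Plateau by Day 5 | 50% | 32-61% | 66-67% |
| Linear ramp | 35% | 21-46% | 33-34% |
| Onset Day 4, then sustained | 69-84% | 50-69% | 60-61% |
| Onset Day 7, then sustained | 74-86% | not tabulated | 29% |
| Days 2-5 only | 69% | 52-79% | 20-21% |

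**Adjusting instead of subtracting.** If the on-CMC mean is compared with the pre-CMC mean as a covariate, power for the step is 87-89%, against 33-46% for Day 11 (between-person share 0.5). Under a ramp or late onset, the adjusted contrast and Day 11 have about equal power.

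**The case against.** **The degrees of freedom are inferred.** This stands. Section 7.2.1 does not say that time is a 12-level factor, and it does not exclude follow-up contrasts. What can be said is that no contrast is specified and that the standard reading gives 11 df.

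**The interaction is not the only fecal test.** This also stands. A reader might infer that it is, but the Day 11 comparison is a valid, directional, randomised comparison. Its limits are that it uses one stool and no baseline, and that it has low power for this effect.

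**The ranking rests on an assumed time course.** This is the strongest objection, and it stands. CMC starts at dinner on Day 1, and the eligibility criteria admit people who pass stool every second day, so a full effect in the Day 2 stool is the case most favourable to the contrast. A two-day delay to Day 4 removes the advantage: uncorrected, the interaction is ahead, and with Greenhouse-Geisser the two are similar. With onset at Day 7 the interaction is clearly better. A reader might infer that the contrast should replace the RM-ANOVA or be the deciding test; the documents state no time course that would support this.

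**The study is exploratory.** Section 3.2 declares no pre-specified efficacy endpoints, and a test open to any pattern is defensible in that setting. This is a reason to keep the RM-ANOVA. It does not remove the need for an estimate of extent.

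**The two pre-CMC stools reflect different diets.** Visit 2 follows the habitual diet, Day 1 the washout. Individual responses to washout add noise that the power model leaves out. The arms remain comparable because both go through the same washout.

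**Conclusion.** The point holds as a gap in the plan that is cheap to close, not as a fault in the RM-ANOVA itself. Section 7.2.1 names no baseline-adjusted estimate of the CMC effect over the intervention period, and that is the quantity Objective 2 needs. For an immediate, sustained shift that one contrast finds with 80% power, the interaction has about 45% (about 28-57% when corrected) and Day 11 alone about 22-46%. This rests on the 11-df reading, a two-sided alpha of 0.05, and assumed effect size, correlation and time course.

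A reader might infer that a real, sustained CMC effect would more often be missed than found by the planned longitudinal test. The figures do not support this in general: the Huynh-Feldt-corrected interaction has 53-57% power at residual correlations of 0.5 and 0.7, and the ratio of the two powers rises to 0.66-0.75 when the contrast has 90-95%. The need for a direction and a size does not depend on any of these power figures.

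**What to change.** In Section 7.2.1, beside the RM-ANOVA and not in place of it, add one pre-specified contrast per principal component: each participant's mean over on-CMC stools (Days 2-11; the same days in the control arm), compared between arms and adjusted for that participant's pre-CMC mean (Visit 2 and Day 1 stools). Report the estimate with its confidence interval. State how time is coded in the RM-ANOVA, so that the degrees of freedom of the interaction are clear.

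The cost is a few sentences of analysis plan and two summary values per participant and component, with no new samples or visits. The downside is one more test per component. The contrast is also less sensitive to delayed or transient effects, which the retained interaction test covers.

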7.2.2 Comparison of metabolites between diets with and without CMC

The first analysis will compare the abundance of fecal and plasma metabolites between the two dietary groups. As assignment to the diet will be based on randomization, the primary analysis will be an unadjusted t-test to compare the concentration of the various metabolites measured in the plasma and feces. As there will be multiple comparisons, we will report both nominal (p values) and q values accounting for the multiple testing.

7.2.3 Effects of CMC consumption on a range of inflammatory and metabolic parameters that characterize metabolic syndrome

Weight change will be compared between the treatment groups from day 1 to day 11 using a t-test. If there is evidence of confounding despite randomization, additional analyses will use linear regression adjusted for change in weight from day 1 to day 11 and BMI at day 0.

We will also assess changes to each subject regarding satiety (from the questionnaire re food adequacy/sufficiency). These data are on visual analogue scale so will be compared using unpaired t-test for between group comparisons or paired t-tests for within group comparisons.

The area under the glucose and insulin concentration curves during the oral glucose tolerance test at day 1, day 11 and the change from day 1 to day 11 will be compared between groups using a t-test. The $\Delta I_{30}/\Delta G_{30}$ will be used as a measure of

beta cell function⁴⁵ while homeostasis model assessment of insulin resistance (HOMA-IR) will be used to estimate insulin resistance⁴⁶ and compared between the groups with a t-test at the same time points.

Sera will be assayed for a range of hormones and cytokines using a customized bead-based assay designed to include immune inflammatory and metabolic markers of obesity and type 2 diabetes (includes IL-8, IL-6, TNF α , lipocalin-2, MCP1, insulin, leptin, ghrelin, ESR, CRP) all of which are known to be elevated in metabolic syndrome (performed at GSU). Additionally, fecal samples will be assayed for lipocalin-2 by ELISA. These data will be compared using unpaired t-test for between group comparisons or paired t-tests for within group comparisons.

8 Safety and Adverse Events

Adverse Event

An **adverse event** (AE) is any symptom, sign, illness or experience that develops or worsens in severity during the course of the study. Intercurrent illnesses or injuries should be regarded as adverse events. Abnormal results of diagnostic procedures are considered to be adverse events if the abnormality:

- results in study withdrawal
- is associated with a serious adverse event
- is associated with clinical signs or symptoms
- leads to additional treatment or to further diagnostic tests
- is considered by the investigator to be of clinical significance

Serious Adverse Event (SAE)

Adverse events are classified as serious or non-serious. A **serious adverse event** is any AE that is:

- fatal
- life-threatening
- requires or prolongs hospital stay
- results in persistent or significant disability or incapacity
- a congenital anomaly or birth defect
- an important medical event

Important medical events are those that may not be immediately life threatening, but are clearly of major clinical significance. They may jeopardize the participant, and may require intervention to prevent one of the other serious outcomes noted above. For example, drug overdose or abuse, a seizure that did not result in in-patient hospitalization or intensive treatment of bronchospasm in an emergency department would typically be considered serious.

All adverse events that do not meet any of the criteria for serious will be regarded as **non-serious adverse events**.

Adverse Event Reporting Period

The study period during which AEs must be reported is normally defined as the period from the initiation of any study procedures to the end of the study treatment follow-up. For this study, the study treatment follow-up is defined as 7 days following the last administration of study diet.

Preexisting Condition

A preexisting condition is one that is present at the start of the study. A preexisting condition should be recorded as an adverse event if the frequency, intensity, or the character of the condition worsens during the study period.

General Physical Examination Findings

At screening, any clinically significant abnormality should be recorded as a preexisting condition. At the end of the study, any new clinically significant findings/abnormalities that meet the definition of an AE must also be recorded and documented as an AE.

Post-study Adverse Event

All unresolved AEs that are categorized by the investigator as definitely or probably related to participation in the study should be followed by the investigator until the events are resolved, the participant is lost to follow-up, or the AE is otherwise explained. At the last inpatient evaluation, the investigator will instruct each participant to report any subsequent event(s) that the participant, or the participant's personal physician, believes might reasonably be related to participation in this study. The investigator will notify the study sponsor of any death or AE occurring at any time after a participant has discontinued or terminated study participation that may reasonably be related to this study. The sponsor should also be notified if the investigator should become aware of the development of cancer or of a congenital anomaly in a subsequently conceived offspring of a participant that has participated in this study.

Abnormal Laboratory Values

A clinical laboratory abnormality should be documented as an adverse event if any one of the following conditions is met:

- The laboratory abnormality is not otherwise refuted by a repeat test to confirm the abnormality
- The abnormality suggests a disease and/or organ toxicity
- The abnormality is of a degree that requires active management; e.g. change of dose, discontinuation of the drug, more frequent follow-up assessments, further diagnostic investigation, etc.

Hospitalization, Prolonged Hospitalization or Surgery

Any AE that results in hospitalization or prolonged hospitalization should be documented and reported as an SAE unless specifically instructed otherwise in this protocol. Any condition responsible for surgery should be documented as an AE if the condition meets the criteria for an AE.

Neither the condition, hospitalization, prolonged hospitalization, nor surgery are reported as an AE in the following circumstances:

- Hospitalization or prolonged hospitalization for diagnostic or elective surgical procedures for a preexisting condition. Surgery should **not** be reported as an outcome of an AE if the purpose of the surgery was elective or diagnostic and the outcome was uneventful.

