6.1.2 Blood sample collection and storage

Blood will be collected after an overnight fast prior to breakfast at the screening visit, at the post-screening visit, and on Days 1-4, 8, 10, and 11 of the inpatient study. Approximately 16cc of blood will be collected for metabolomics at each collection. Plasma will be separated from the blood samples. The plasma will be stored frozen at minus 80°C for use in metabolomic studies. Peripheral blood monocytes (PBMCs) will also be collected from the same samples and stored at minus 80°C for potential future use in cell phenotyping studies.

Participants may be contacted and asked to return 1 month after discharge for a follow-up blood collection.

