6.2.4.6 Sample collection

Blood, urine, and feces samples will be obtained. Up to 15 ml of urine samples will be collected prior to 09:00h after an overnight fast starting at midnight. Approximately 16cc of blood will be collected for metabolomics at each collection following an overnight fast prior to breakfast. Participants will be provided a stool collection kit to collect a stool sample on the day prior to admission or on the morning of admission. The first stool sample will be weighed, aliquoted and frozen. Participants will collect stool from all subsequent bowel movements. This stool will be weighed, the weight recorded and discarded. In addition, a stool sample will be collected by the participant at home either the day prior to Visit 3 or the morning of Visit 3. Participants will bring the stool sample to the visit. Study staff will provide the participant with collection materials and instructions for collecting the stool at home and returning it to study staff (See section 6.1.3).

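### The between-arm tests for metabolites, serum markers and fecal lipocalin-2 make no stated use of the pre-CMC sample already collected, which gives up precision at 8 per arm

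*Combined protocol and SAP*

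**What the plan says.** Section 7.2.2 compares fecal and plasma metabolites between the arms. Citing randomization, it states that "the primary analysis will be an unadjusted t-test to compare the concentration of the various metabolites measured in the plasma and feces". Both nominal p values and q values will be reported. No sampling day, baseline term or change score is named.

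For serum hormones, cytokines and CRP, and for fecal lipocalin-2, Section 7.2.3 says: "These data will be compared using unpaired t-test for between group comparisons or paired t-tests for within group comparisons". It does not name the day, or say whether the unpaired test is on a value or a change. Section 6.4.5 ties Day 11 to the comprehensive metabolic panel and names no day for the hormones and cytokines.

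Other parts of Section 7.2.3 are more specific. Weight is tested as change, and the glucose tolerance areas "at day 1, day 11 and the change from day 1 to day 11 will be compared between groups using a t-test". The only regression in that section is conditional, and it adjusts for weight change and BMI rather than for the marker's own baseline.

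Pre-CMC samples are planned. Section 6.1.2 schedules fasting blood at screening, "at the post-screening visit, and on Days 1-4, 8, 10, and 11 of the inpatient study". Section 6.2.4.6 has a stool "collected by the participant at home either the day prior to Visit 3 or the morning of Visit 3". Section 5 says that "no emulsifiers will be consumed prior to dinner on Day 1".

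Section 7.1 gives 80% power under Aim 3 for a between-group difference of 1.51 SD. It does not say which SD is meant.

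**The concern.** With 8 participants per arm, differences between people in metabolite and cytokine levels make up much of the noise in a comparison of Day 11 values. Some of that noise was already present before CMC and can be removed by adjusting for the pre-CMC value. The samples needed are collected anyway. A plan that leaves them out of the between-arm test detects only very large effects, and may miss moderate ones that the same participants could have shown. The within-arm paired tests do use an earlier value, but they do not compare the arms and cannot replace an adjusted comparison.

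**Working it through.** **Inputs.** 8 per arm (Sections 5 and 7.1); 80% power and 1.51 SD (Section 7.1, Aim 3). Assumed: two-sided alpha 0.05, normal data, equal variances, and a baseline-to-Day 11 correlation ρ from 0 to 0.8. Applying the Aim 3 figure to metabolites is also an assumption.

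**The plan's own figure.** Unadjusted t-test: SE = √(2/8) = 0.50 SD, 14 df. At 1.51 SD the noncentrality is 1.51/0.50 = 3.02 and power is 80.2%; the exact detectable difference is 1.507 SD. The plan's figure reproduces. Power at 1.0 SD is 46%.

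**ANCOVA.** SE = √[(1 − ρ²)(2/8)(1 + F/14)], 13 df, averaged over F ~ F(1, 14) to allow for chance baseline imbalance. The mean of F is 14/12, so the average variance factor is 1 + 1/12 = 13/12.

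**Change score**, for comparison: the t-test figure times √[2(1 − ρ)].

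| ρ | t-test on Day 11 value: detectable SD | Change score: detectable SD | ANCOVA: detectable SD | ANCOVA power at 1.0 SD (t-test 46%) |
|---|---|---|---|---|
| 0 | 1.51 | 2.13 | 1.57 | 43% |
| 0.3 | 1.51 | 1.78 | 1.50 | 47% |
| 0.5 | 1.51 | 1.51 | 1.36 | 54% |
| 0.7 | 1.51 | 1.17 | 1.12 | 70% |
| 0.8 | 1.51 | 0.95 | 0.94 | 84% |

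At ρ = 0.7 the variance factor is 0.51 × 13/12 = 0.55, equivalent to about 8/0.55 = 14.5 participants per arm without adjustment.

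**Break-even and worst case.** At a 1.0 SD difference ANCOVA equals the t-test at ρ of about 0.28. The largest loss, at ρ = 0, is 3.7 power points. Simulation (40,000 trials per setting) gave ANCOVA power of 43, 47, 54, 71 and 84%, with type I error of 4.9 to 5.2%.

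**Stricter threshold.** Metabolites are also judged on q values. At an assumed per-test level of 0.005 the t-test detects 2.13 SD, and ANCOVA 2.24, 2.14, 1.94, 1.60 and 1.35 SD at the same ρ values. Break-even is about 0.31 and the largest loss 5.7 points.

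**Missing baseline stool.** If one participant per arm lacks a baseline and is dropped, ANCOVA on 7 per arm detects 1.72, 1.64, 1.49, 1.23 and 1.03 SD. Break-even against the t-test on 8 rises to about 0.48, and the largest loss to about 11 points. Filling the gap with the pooled baseline mean keeps all 16. At ρ = 0.3 and 1.0 SD, power is then 46% against 41% when dropped, with type I error about 5%. That advantage narrows as ρ rises and is gone by about 0.8.

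**Noisy stool covariate.** Effective ρ = ρ × √reliability. At assumed reliabilities of 0.8, 0.6 and 0.4, a ρ of 0.7 becomes 0.63, 0.54 and 0.44, and a ρ of 0.5 becomes 0.45, 0.39 and 0.32. All stay above 0.28. A ρ of 0.3 becomes 0.27, 0.23 and 0.19, which falls below it.

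**The case against.** The unadjusted test is a legitimate choice with a stated reason. Section 3.2 says that this is not an efficacy study and has no pre-specified efficacy or safety endpoints. The gain depends on a correlation that the documents do not give. All of this stands, and it limits the point to a recommended improvement. It does not remove it: Section 7.2.2 itself names a primary analysis, Section 7.1 claims power for Aim 3, and the worst-case loss from adjusting is small.

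The fecal measures are the weaker case. Home collection may lower the correlation, and dropping participants without a baseline stool could make ANCOVA worse than the t-test. Filling with the pooled mean largely answers the second objection; the first remains. A missing Day 11 stool is also possible, since discharge may come by 5pm, but it costs both analyses the same participant.

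Some stronger readings are not supported:

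- A reader might infer that the t-test is biased or invalid. Under randomization it is neither.
- A reader might infer that the unnamed day and quantity are themselves a serious flaw. They are missing detail. The satiety paragraph, which begins "We will also assess changes to each subject regarding satiety", uses similar test wording, so a test on change is a possible reading for the serum markers and lipocalin-2. ANCOVA is at least as precise as a change score throughout the table, so the recommendation holds either way.
- A reader might take the general rule in Section 6.1.3, "They will then arrange a drop-off time with the study coordinator within 48 hours of sample collection", to mean that the baseline stool waits up to two days. Section 6.2.4.6 has that stool collected the day before or the morning of admission and brought to the visit, and Section 6.1.3 has a portion put in ethanol at once.
- A reader might infer that serum markers and lipocalin-2 are assayed only on Day 11. The planned paired tests need at least two time points.

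**Conclusion.** The point holds as a loss of precision, and the remedy is a cheap improvement. With 8 per arm and two-sided 0.05, the detectable difference falls from 1.51 SD to about 1.36 SD at a correlation of 0.5 and 1.12 SD at 0.7. It is essentially unchanged at 0.3 (1.50 SD) and slightly worse at 0 (1.57 SD). This assumes normal data, equal variances, complete baselines and one correlation for every analyte. The case is firmest for plasma metabolites and serum markers, where the baseline is a fasting Day 1 sample with the same specified fasting and collection conditions as Day 11. For the fecal measures the direction is the same but the gain is less certain.

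**What to change.** - **Plasma metabolites and serum markers:** make the primary between-arm analysis an ANCOVA of the Day 11 value on arm plus the fasting Day 1 value. Compute the metabolite q values from that model. Keep the unadjusted t-test as a sensitivity analysis.
- **Fecal metabolites and lipocalin-2:** use the same model, with the post-washout stool collected the day before or the morning of admission as the named baseline. Fill a missing baseline with the mean of the observed baselines over both arms, so that no randomized participant with an outcome is dropped. State that home handling may reduce the gain.
- **Interpretation:** base conclusions about CMC on the between-arm estimate, and treat the within-arm paired tests as descriptive.

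The cost is plan wording, one degree of freedom, and a small loss of power if the correlation is below about 0.3. Stored Day 1 samples would need metabolite assay if that is not already planned. The documents do not say which days are assayed for metabolites; for serum markers and lipocalin-2 the paired tests already imply at least two time points. No new visit or sample is needed.
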